10.2 SAMPLE SIZE DETERMINATION

Initially, the planned sample size is a minimum of 4 evaluable patients (2 per arm) and a maximum of 48 evaluable patients (24 evaluable patients maximum per arm). As of amendment version dates 04/13/2021 and 10/12/2021, determination has been made not to escalate either arm to dose level 3. Accordingly, a maximum of 42 evaluable patients may be enrolled (21 evaluable patients maximum per arm). Estimates for sample size are based on the assumption that all dose levels will accrue a maximum of patients, thus sample size is likely over-estimated. We do not anticipate drop out during treatment or follow-up, however that remains a possibility. We anticipate drop out would be minimal as we tend to accrue these patients from mainly the local area. To allow for a small number of patients who drop out or are not evaluable, we will set the accrual ceiling at 46.

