3 STUDY IMPLEMENTATION

3.1 STUDY DESIGN

Patients with locally recurrent prostate cancer following radiotherapy will be enrolled in this study if they have no evidence of distant metastatic disease on staging studies. If abnormalities are noted on bone scan and/or NaF PET/CT, the results of these studies will be reviewed by the PI and radiology/nuclear medicine colleagues. On a case by case basis, the likelihood of metastasis will be determined if evidence of abnormalities is visible. In general, NaF PET will be considered more sensitive. Multiparametric MRI of the prostate and 18F-DCFPyL imaging will be obtained to assess for areas of local recurrence. Patients found to have regional adenopathy that is distant to the prostate or metastatic disease at other sites on staging studies such as 18F-DCFPyL will undergo biopsy confirmation if clinically appropriate to confirm metastatic disease and will be removed from the study and replaced if metastases are confirmed. Patients deemed to have a non-metastatic local recurrence will undergo targeted (research and diagnostic) and systematic biopsies of the prostate (diagnostic) to confirm areas of recurrence and correlate imaging with pathology. Areas noted to have uptake on 18F-DCFPyL imaging will also be biopsied if they represent areas not seen on MRI. During the same procedure, fiducials to guide radiotherapy will be placed if not previously placed or visible. Approximately one week after fiducial placement or biopsy (if fiducial placement not required), patients will undergo treatment planning for SBRT.

There will be two Cohorts in this trial. Cohort 1 includes patients with prior EBRT for the treatment of prostate cancer. These patients may have received ADT with EBRT but have not received brachytherapy. Patients enrolled in Cohort 2 will have received brachytherapy of the prostate as a component of the initial radiation treatment (either alone or in combination with EBRT and/or ADT). See section [2.3.1](#).

SBRT will be delivered to areas of recurrent prostate cancer identified on imaging and biopsy (all patients, Arms 1 and 2) and a reduced dose will be delivered to the entire prostate (Arm 2). The low dose total prostate exposure is used in Arm 2 as MR imaging may be moderately compromised in after prior brachytherapy.

Table 2: Dose Levels

| | Arm 1: Tumor Irradiation | | Arm 2: Prostate and Tumor Irradiation | |

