3.1.2 Dose Escalation

Dose escalation will proceed in parallel in Arm 1 (Tumor Irradiation) and Arm 2 (Prostate and Tumor Irradiation) in groups of 3–6 patients. The MTD is the dose level at which no more than 1 of up to 6 patients experience DLT during treatment and up to 3 weeks following completion of treatment, and the dose below that at which at least 2 (of ≤ 6) patients have DLT as a result of treatment. If a patient did not experience DLT and did not finish treatment, he will not be evaluable for toxicity and will be replaced in the dose level (See [Table 2](#)).

Dose escalation will follow the rules outlined in [Table 3](#) below for each Arm (1 or 2) independently as MTD and toxicities are expected to be different as a result of prior treatment.

Table 3: Escalation Decision Rule

| Number of Patients with DLT at a Given Dose Level | Escalation Decision Rule |
|---|--|
| 0 out of 3 | Enter up to 3 patients at the next dose level |
| ≥ 2 | Dose escalation will be stopped. This dose level will be declared the maximally administered dose (highest dose administered). Up to three (3) additional patients will be entered at the next lowest dose level if only 3 patients were treated previously at that dose. |
| 1 out of 3 | Enter up to 3 more patients at this dose level. 
• If 0 of these 3 patients experience DLT, proceed to the next dose level.• If 1 or more of this group suffer DLT, then dose escalation is stopped, and this dose is declared the maximally administered dose. Up to three (3) additional patients will be entered at the next lowest dose level if only 3 patients were treated previously at that dose. |
| ≤ 1 out of 6 at highest dose level below the maximally administered dose | This is the MTD and is generally the recommended phase 2 dose. 6 additional patients may be entered at the recommended phase 2 dose. |

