10.4 STATISTICAL ANALYSES

10.4.1 General Approach

This is a phase I study. There are two arms to this study for 1) patients with prior brachytherapy as a component of their treatment for prostate cancer, and 2) patients with prior EBRT without brachytherapy. Arms are enrolled and escalated separately. Groups of 3-6 patients are evaluated at each dose level. The dose level on which 2 patients experience unacceptable toxicity is considered to have exceeded the MTD. The next lower dose level on which no more than 1/6 patients experience unacceptable toxicity is considered the MTD for each arm of the study.

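### The amended maximum of 42 evaluable patients (21 per arm) does not follow from the plan's own rules, which give 36 (18 per arm) once dose level 3 is dropped; the accrual ceiling of 46 inherits the discrepancy

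*Combined protocol and SAP*

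**What the plan says.** Section 10.2 gives an initial upper limit of "a maximum of 48 evaluable patients (24 evaluable patients maximum per arm"). It then notes that, under the amendments dated 04/13/2021 and 10/12/2021, neither arm will go to dose level 3, and draws the consequence: "Accordingly, a maximum of 42 evaluable patients may be enrolled (21 evaluable patients maximum per arm"). The basis of the count is given as "Estimates for sample size are based on the assumption that all dose levels will accrue a maximum of patients", and the section adds that the size is for this reason probably an over-estimate. Losses are handled in a separate step: "To allow for a small number of patients who drop out or are not evaluable, we will set the accrual ceiling at 46". The Précis repeats the 46.

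The numbers behind the count are in other sections:

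- Per dose level, Section 10.4.1: "Groups of 3-6 patients are evaluated at each dose level". Section 10.4.5 repeats the range of 3 to 6 and exempts only the expansion cohort.
- Expansion, last row of Table 3 in Section 3.1.2: "6 additional patients may be entered at the recommended phase 2 dose".
- Section 1.2.5 announces the expansions in both arms but gives no size for them.

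**The concern.** Section 10.2 presents 42 as the result of removing one dose level. A level assumed to be full holds 6 patients per arm, but the stated maximum falls by only 3 per arm, from 24 to 21. The initial and amended figures therefore do not come from the same counting rule.

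The maximum limits how many men may be re-irradiated in a Phase I trial, and the ceiling approved for enrolment rests on it. As written, three patients in each arm belong neither to a dose level nor to the expansion, and no purpose is given for them.

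**Working it through.** **Inputs**

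| Quantity | Value | Source |
|---|---|---|
| Arms, escalated separately | 2 | Sections 3.1.2, 10.4.1 |
| Dose levels per arm, initially | 3 | Table 2 |
| Dose levels per arm, after the amendments | 2 | Table 2 footnote, Section 10.2 |
| Maximum per level | 6 | Sections 10.4.1, 10.4.5 |
| Expansion per arm | 6 | Table 3 |
| Accrual ceiling | 46 | Section 10.2, Précis |

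**Formula.** Maximum = arms × (levels × 6 + expansion).

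**Step 1: reproduce the initial figure.** 3 × 6 + 6 = 24 per arm, and 2 × 24 = 48. Both match Section 10.2. The initial minimum of 2 per arm also fits Table 3 (DLT in the first two patients treated), so Section 10.2 does appear to be a count from Table 3.

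**Step 2: drop one level.** 2 × 6 + 6 = 18 per arm, and 2 × 18 = 36. Section 10.2 states 21 and 42. The excess is 42 − 36 = 6 patients, or 6/36 = 16.7%. Following every path through Table 3 gives a per-arm maximum of 24 with three levels and 18 with two; no two-level path reaches 21.

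**Step 3: look for a reading that rescues 21.**

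- *The same rule before and after.* With m per level and e in expansion, 3m + e = 24 and 2m + e = 21 give m = 3 and e = 24 − 9 = 15. The plan has 6 and 6.
- *An expansion of 9.* 2 × 6 + 9 = 21, but Table 3 says 6. An expansion of 9 from the start would have made the initial maximum 3 × 6 + 9 = 27.
- *The up to three further patients at the next lower level in Table 3.* They enter only if that level had 3 patients. They fill it to 6 and add nothing beyond.
- *Loss allowance inside the 42.* Raising 36 to 42 would need 1 − 36/42 = 14.3% losses. But 42 is stated as evaluable patients, and losses are added afterwards to reach 46.

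**Step 4: the ceiling.** The documents give no loss rate. The implied allowance is 46 − 42 = 4, or 4/46 = 8.7% of enrolment.

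| Allowance on 36 evaluable | Ceiling |
|---|---|
| 4 patients, as implied now | 36 + 4 = 40 |
| 8.7%, as implied now | 36/0.913 = 39.4, so 40 |
| 10% (assumed) | 36/0.90 = 40 |
| 15% (assumed) | 36/0.85 = 42.4, so 43 |
| 20% (assumed) | 36/0.80 = 45 |

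Keeping 46 over 36 would mean an allowance of 10, or 10/46 = 21.7% of enrolment. That is hard to square with a section that expects minimal drop-out and provides for only a small number of lost patients.

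**The case against.** The strongest defence is that the expansion size changed with the amendments. Section 10.2 separates the initial figure from the amended one, and Section 1.2.5 ties the expansions to the same amendments. An expansion of 6 at first and 9 later would give 24 and then 21. The Arm 2 expansion was also decided on judgement, with three patients treated at each of two levels and no maximally administered dose reported, so it is open to argument whether the last row of Table 3 governs its size. This stands to the extent that the solution m = 3, e = 15 and the figure of 27 both assume an unchanged expansion size, and that the documents do not settle which section is wrong. It does not remove the mismatch: no section states 9, Table 3 still says 6, and if 9 was meant then Table 3 needs correcting.

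A second point is that 36 may itself be too high. Section 1.2.5 reports three Arm 2 patients at level 1 and expansion at level 2. If no more enter level 1, Arm 2 can reach only 3 + 6 + 6 = 15, or 33 in total with 18 in Arm 1. That is true of accrual to date, but Section 10.2 counts on the basis that every level fills, and on that basis the figure is 36. The remark that the size is probably over-estimated belongs here too. It explains why actual enrolment may fall below the maximum, not why the maximum exceeds what the rules allow.

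Third, the consequences are limited. A ceiling permits enrolment without requiring it, there is no power calculation to upset, and the documents supply no loss rate, so 40 is no better founded as a ceiling than the rate assumed for it. All of this is fair. It keeps the point to a correction of the stated size and does not make 42 right.

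**Conclusion.** The concern holds. Under the per-level cap of 6, an expansion of 6 and two remaining levels, the maximum is 18 evaluable patients per arm and 36 in total. The stated 21 and 42 are too high by 3 and 6. The counting rule is confirmed by its exact reproduction of 24 and 48.

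The result rests on Table 3 being the current statement of the expansion size, which is the only size the documents give. Subtracting 3 instead of 6 per arm is a plausible source of the error, but this is not documented. Confidence in the mismatch is high; which section needs correcting is for the sponsor to say. The MTD decision rule does not change. The correction should be made because a stated sample size and the enrolment ceiling built on it are not supported by the plan.

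**What to change.** 1. In Section 10.2, restate the maximum as 36 evaluable patients (18 per arm) and show the count: two levels of 6 plus an expansion of 6.
2. If 21 per arm is intended, keep it, amend Table 3 to agree, and state what the extra 3 per arm are for, for example a larger expansion cohort. Give the expansion size in Section 1.2.5 as well.
3. Re-derive the accrual ceiling from the reconciled maximum, and change it in both Section 10.2 and the Précis. State the allowance and its basis. It should cover drop-out and two kinds of replacement the plan already provides for: the patient who stops treatment without DLT, of whom Section 3.1.2 says "he will not be evaluable for toxicity and will be replaced in the dose level", and patients who under Section 3.1 "will be removed from the study and replaced if metastases are confirmed".

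The cost is a short text amendment to Section 10.2 and the Précis, and to Table 3 and Section 1.2.5 if a larger expansion was meant. The one risk is setting the new ceiling so tight that replacements cannot be entered, so it should leave room for every evaluable place to be filled.

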10.3 POPULATIONS FOR ANALYSES

All enrolled patients that initiate treatment with SBRT will be considered evaluable for toxicity. Patients that complete at least one post-treatment PSA will be considered evaluable for biochemical control and biochemical relapse free survival. Patients that complete QoL measures at 3 months will be considered evaluable for these measures. Patients undergoing biopsy following DCFPyL studies will be considered evaluable for the sensitivity and positive predictive value of this study regardless of whether treatment is received.

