3.6 STUDY CALENDAR

| Procedure | Screening/ Baseline | Active SBRT treatment | Post Therapy Follow-up (1, 3 mos) 15 | Post Therapy Follow-up 6 months post-SBRT | Post Therapy Follow-up (9 mos and q 3 mos until 24 mos) 8 | |
|--|------------------------|-----------------------------|---|--|---|--|
| History and PE | X | | | | | |
| Vital signs 10 | X | | X | X | X | |
| Performance Score | X | | | | | |
| Weight | X | | | | | |
| Labs | | | | | | |
| CBC, Acute care panel, LFTs, Testosterone, PT/PTT, Viral serologies 2 | X | | | | | |
| PSA 4 | X | | X 11 | X 11 | X 11 | |
| Biopsies (ultrasound guided)/fiducials 5 | X | | | | | |
| mpMRI 3 | X 3 | | | X 12 | | |
| 18F-DCFPyL PET/CT imaging | X 7 | | | X 6, 12 | | |
| 18F-NaF PET/CT imaging 3 | X | | | | | |
| Whole body bone scan 3 | X | | | | | |
| Clinical evaluation | | X | X 9 | X 9 | X 9 | |
| Adverse Events | X | | Monitored continuously | | | |
| Concomitant Medications | X | | Monitored continuously | | | |
| Correlatives | | | | | | |
| Research Biopsy 5 | X | | | | | |
| Blood 12 | X | X 1 | X | X | X | |
| Urine 12 | X | | X | X | X | |
| Questionnaires | | | | | | |
| EPIC-26, SHIM, AUA-SI, DRS, PROMIS 13, 14 | X | | X | X | X | |

1. Correlative blood sampling should be performed within 24 hours after the last dose of irradiation.
2. CBC with differential, chemistries (to include creatinine BUN, PSA, testosterone, Alk Phos, ALT, AST, Bilirubin), PT, PTT within 4 weeks of study entry. Viral serologies: HIV, Hepatitis B, and Hepatitis C screening within 4 weeks of study entry. Acute Care Panel: (Sodium (NA), Potassium (K), Chloride (CL) Total CO₂ (Bicarbonate), Creatinine, Glucose, Urea nitrogen, eGFR).
3. Whole body bone scan, F18 NaF PET, and multiparametric MRI of the prostate. In selected patients, a CT of the abdomen and pelvis (with oral and IV contrast) may also be obtained for staging, particularly if MRI is not felt to adequately have staged the pelvic and abdominal lymph nodes. All imaging studies should be completed within 3 months prior to study entry. MRI of the prostate obtained more than 3 months (no greater than 5 months prior to entry) may be used if a biopsy has recently been performed, as post-biopsy MRI may not be easily interpretable due to hemorrhage.

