3.10.3 Lost to Follow-up

A participant will be considered lost to follow-up if he or she fails to return for 3 scheduled visits and is unable to be contacted by the study site staff.

The following actions must be taken if a participant fails to return to the clinic for a required study visit:

- The site will attempt to contact the participant and reschedule the missed visit and counsel the participant on the importance of maintaining the assigned visit schedule and ascertain if the participant wishes to and/or should continue in the study.
- Before a participant is deemed lost to follow-up, the investigator or designee will make every effort to regain contact with the participant (where possible, 3 telephone calls and, if necessary, an IRB approved certified letter to the participant's last known mailing address or local equivalent methods). These contact attempts should be documented in the participant's medical record or study file.
- Should the participant continue to be unreachable, he or she will be considered to have withdrawn from the study with a primary reason of lost to follow-up.

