10 STATISTICAL CONSIDERATIONS

This is a single-institution, two-arm, Phase I trial, where patients with locally recurrent prostate cancer after prior radiotherapy will receive image-guided, focally dose escalated SBRT to the sites of local recurrence. Patients will be treated with escalated doses of radiation with the escalation on each arm occurring in parallel, and inclusion on each arm based on prior radiation treatment received. The primary endpoints will be to define the MTD of this approach. The secondary endpoints include to define DLTs, to describe the rate of 1 and 2-year biochemical relapse free survival (Phoenix criteria), to evaluate DCFPyL imaging as a method to detect locally recurrent prostate cancer after irradiation, and to define the quality of life changes that occur during and after this treatment. Exploratory endpoints include description of decision regret in patients who failed treatment and are successfully or unsuccessfully salvaged, evaluation of a personalized mutation panel for detection of early recurrence, and evaluation for the presence of neuroendocrine markers and markers of resistance in radio-recurrent prostate cancer.

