10.4.7 Exploratory Analyses

- Evaluate the feasibility of a patient specific circulating cell free DNA (cfDNA) mutation panel for predicting biochemical recurrence. We will first perform whole exome sequencing on the biopsy tissue acquired at baseline, and use that sequencing data to derive data on somatic mutations and somatic copy number alterations. We will also perform low-pass whole genome sequencing on total DNA extracted from plasma. Mutations detected in prostate biopsies harboring tumor that are not found in germline considered as potential contributors to each patient's individualized mutation panel. We will make direct comparisons whether a subset or all of the copy number alterations or mutations detected during baseline are represented in plasma prior to treatment. This will be reported as a binomial proportion (percent of patients with some or all of the panel detected and percent that have none of the panel detected). These same mutations defined from pretreatment

samples (evident in pretreatment plasma) will be evaluated in cfDNA (plasma) at each time point of follow up. Direct comparisons of whether a subset or all of the copy number alterations or mutations detected at baseline are represented in plasma will be performed and reported as a binomial proportion (percent of patients with some or all of the panel detected and percent that have none of the panel detected). We hypothesize that patients experiencing relapse will show mutations and copy number alterations present in cfDNA, versus responders where ctDNA would comprise a very small (if any) proportion of the total cfDNA. Because radiation may not kill cells immediately, but can result in late necrosis or mitotic catastrophe, it is not known what the optimal time point for analyzing a “nadir” in detectable mutations is or if one will be detected. Thus, this is an exploratory and descriptive project.

- Evaluate decision regret at the time of enrollment and at the end of follow up relating to the primary treatment for prostate cancer to determine if successful salvage mitigates decision regret. The percentage of patients scored as having decision regret will be compared to the percentage of patients not exhibiting decision regret (regarding the initial radiation treatment). It is hypothesized the effective salvage therapy will mitigate decision regret expressed at the time of enrollment.

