11.4.1.10 Questionnaire Risks

Questionnaires may contain questions that are sensitive in nature. The participants are asked to only answer questions they are comfortable with.

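### The only stated quality-of-life population requires the 3-month questionnaire, so it excludes usable data from nine other occasions; and the stated decision-regret comparison sets a percentage against its own complement

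*Combined protocol and SAP*

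**What the plan says.** **QoL population.** Section 10.3 states: "Patients that complete QoL measures at 3 months will be considered evaluable for these measures". No other QoL population appears. Section 6.3.1 defines evaluability for toxicity and response only, and Section 10.4.3 adds neither a population nor a missing-data rule for QoL.

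**QoL data and model.** The questionnaire row of the study calendar (Section 3.6) reads "EPIC-26, SHIM, AUA-SI, DRS, PROMIS 13, 14 | X | | X | X | X". Its columns cover baseline, 1 and 3 months, 6 months, and every 3 months from 9 to 24 months. Section 10.4.3 summarises SHIM, AUA Symptom Index and EPIC-26 at baseline and at each visit, and models them with a linear mixed model with random intercept and slope. The hypotheses in Section 10.1 extend to 2 years.

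**Follow-up.** Under Section 3.10.3 a patient is lost only if he "fails to return for 3 scheduled visits and is unable to be contacted by the study site staff".

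**Decision regret.** Section 10.4.7 sets the aim as regret at enrolment and at the end of follow-up, and hypothesises that "effective salvage therapy will mitigate decision regret expressed at the time of enrollment". Section 10 describes the endpoint as "description of decision regret in patients who failed treatment and are successfully or unsuccessfully salvaged". The one comparison specified in Section 10.4.7 is: "The percentage of patients scored as having decision regret will be compared to the percentage of patients not exhibiting decision regret".

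**The concern.** **(A)** A mixed model lets patients with incomplete series contribute what they have. Requiring one particular post-treatment form works against that. A patient can miss month 3, remain in follow-up and supply every other questionnaire, yet fall outside the only population the plan names. Patient-reported outcomes are a secondary objective, the trial is small, and the plan states no benefit from the exclusion.

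**(B)** The regret objective is about change over time and about whether successful salvage explains it. A comparison of those with regret against those without uses neither the two time points nor the salvage groups. Followed literally, it would produce a result that leaves the question unanswered.

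**Working it through.** The plan gives no QoL or regret rate, standard deviation or missing-form rate, so it has no figure of its own to reproduce. Everything marked *assumed* is for illustration.

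**(A) QoL population**

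1. Occasions from Section 3.6: 1 (baseline) + 2 (1, 3 months) + 1 (6 months) + 6 (9, 12, 15, 18, 21, 24 months) = 10 per patient.
2. Patients, Section 10.2: "a maximum of 42 evaluable patients may be enrolled". Scheduled occasions: 42 × 10 = 420.
3. A patient who misses only month 3 can supply up to 9 occasions. Under the rule he supplies none.
4. *Assumed* share missing only that form:
   - 5%: 42 × 0.05 = 2.1, about 2 patients, up to 2 × 9 = 18 occasions
   - 10%: 42 × 0.10 = 4.2, about 4 patients, up to 36 occasions
   - 20%: 42 × 0.20 = 8.4, about 8 patients, up to 72 occasions (72/420 = 17%)
5. Taking the standard error of a visit mean as proportional to 1/√n, its rise at another visit is at most:
   - √(42/40) = 1.025, or 2.5%
   - √(42/38) = 1.051, or 5%
   - √(42/34) = 1.111, or 11%

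   These are upper bounds, because they suppose that every excluded patient completed the other visit.
6. Bias. *Assume* that the worse half at 3 months miss the form 30% of the time and the better half 10%. The retained fractions are 0.35 and 0.45 of all patients. With normal scores (half-means ∓0.798 SD), the retained 3-month mean shifts by d = (0.45 × 0.798 − 0.35 × 0.798)/0.80 = 0.0998 SD.
   - Level at another visit: r × d × SD. With SD 10 and r = 0.3, 0.5, 0.7 this is 0.30, 0.50, 0.70 points.
   - Change from baseline: excluding a patient also removes his baseline form. With one common correlation r, baseline shifts equally, so the bias is (r − r) × d × SD = 0.
   - If the other visit correlates with month 3 by 0.2 more than baseline does: 0.2 × 0.0998 × 10 = 0.2 points.
   - For scale, the standard error of a visit mean is 10/√42 = 1.5 points.

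**(B) Decision regret**

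1. Let p be the percentage with regret at one time. The stated contrast is p − (1 − p) = 2p − 1, which depends on p at that time alone.
2. *Assumed* counts: 12 of 42 with regret at the end. The contrast is 28.6% against 71.4%, or −42.9 points, whatever happened earlier:
   - 6/42 at enrolment: change +14.3 points
   - 12/42 at enrolment: change 0
   - 24/42 at enrolment: change −28.6 points
3. The same 12 patients fit opposite salvage patterns. With 34 controlled and 8 failed: 4/34 and 8/8 (12% and 100%), or 10/34 and 2/8 (29% and 25%).
4. Size of the failure group. With 2-year control of 82%, as in the SBRT series in Section 1.2.1: 42 × 0.18 = 7.6. With the 75% brachytherapy rate in Section 10.1: 42 × 0.25 = 10.5. That is about 8 to 10 patients. An observed 4/8 has an exact 95% interval of 16% to 84%.

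**The case against.** **The population rule does not say it is exclusive.** Section 10.3 omits the word *only*, whereas Section 6.3.1 uses it for response, and Section 10.4.3 excludes nobody. The analyst may therefore use all forms. That is fair as far as it goes: the documents do not show that data will be discarded. But no other QoL population is stated, and the evident use of an evaluability rule is to decide who is analysed.

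**Missingness at 3 months may be low.** Section 3.10 asks for effort to obtain a safety visit at about 90 days before a patient leaves the study. The calendar notes allow remote visits and electronic questionnaires, and Section 10.2 expects minimal drop-out and calls its own sample size likely over-estimated. This stands, and it points to the low end of the 5% to 20% range.

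**A reader might infer that the rule biases the QoL results.** The documents do not support that. The shift computed above is in the mean level at a visit. The plan estimates change, for which the shift cancels under a single within-patient correlation and is small under a modest departure from it.

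**The regret sentence may be shorthand.** Its own bullet names both time points and salvage success, so reporting percentages at both times may be intended. If so, the difference between the two contrasts would be (2p₁ − 1) − (2p₀ − 1) = 2(p₁ − p₀), which does carry the change. A reader should therefore not conclude that the investigators will ignore time or salvage outcome. The sentence nevertheless specifies no time point, pairing or split.

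**Conclusion.** Both parts hold, at modest size.

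**(A)** Applied as written, the only stated QoL population excludes patients whose other forms the planned model could use. The loss is one of information: about 2 to 8 of at most 42 patients, and standard errors at other visits higher by up to about 2.5% to 11%. This rests on an assumed 5% to 20% missing only the 3-month form and on full completion elsewhere. The actual share is not given and may be near the lower figure. No material bias in change from baseline is claimed.

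**(B)** The stated regret comparison cannot by itself show whether regret fell, rose or stayed the same, or whether it differs by salvage outcome. That follows from the algebra and needs no assumed rate. It concerns an exploratory objective.

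The MTD is unaffected. Four neighbouring gaps might be read as further defects, but they are clarifications only and not part of this point: scoring of partly answered forms (Section 11.4.1.10 says "The participants are asked to only answer questions they are comfortable with"), the cut-off for regret, how time enters the model, and the mention of QoL during treatment when that calendar cell is blank. The separate questionnaire manual cited in Appendix B may settle the first two.

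**What to change.** **Section 10.3:** define the QoL population as every patient who started SBRT and has at least one QoL form. State that all available visits enter the mixed model in Section 10.4.3.

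**Section 10.4.7:** replace the percentage comparison with the paired within-patient change in Decision Regret Scale score from enrolment to end of follow-up. Describe it separately for patients with biochemical control and with biochemical failure. Keep the split descriptive, since the failure group would be only about 8 to 10 patients.

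**Cost:** wording in the statistical section only. The questionnaires, including the Decision Regret Scale, are already scheduled at baseline and through 24 months, so no patient, visit or assessment is added.
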